2.5 Outcome measures and times of assessments

Details of all outcome definitions and times of assessments are defined in table below.

Outcome definitions and times of assessments for the primary and secondary objectives

Objective	Definition	Time of assessment
Primary	Proportions of clinically insignificant cancers* Arm 1 vs Arm 2+3*	After completion of screening-round 1 (only screening visits in round 1 are analysed). Next assessment includes all screening visits up to 30 th June 2022 and 2, 6 and 10 years thereafter
Secondary	Proportions of clinically significant cancers* Arm 1 vs Arm 2+3*.	After completion of screening-round 1 (only screening visits in round 1 are analysed). Next assessment includes all screening visits up to 30 th June 2022 and 2, 6 and 10 years thereafter
Additional 1)	Proportions of clinically significant cancers Arm 2 vs Arm 3. See separate protocol	Including men who were invited and participated up to 30 th June 2024 and 2, 6 and 10 years thereafter
Additional 2)	Cancer-specific incidence and mortality SG vs CG (intention to screen analysis). See separate protocol	12 years after randomization (31 December 2027) and every third year after.
Additional 3)	Sensitivity and specificity comparing multi- versus bi-parametric MRI. See separate protocol	After completion of screening round 1

SR = screening round. SG = Screening group. CG = control group

* The first analysis based upon screening round 1 will also include men in arm 3 ignoring cancers detected in the PSA range 1.8-2.99 and group them together with men in arm 2, but analysis coming after that including also subsequent screening rounds will only compare arm1 versus arm 2.

The primary definition of clinically significant PC is Gleason¹ Score $\geq 3 + 4$ (also known as Grade Group 2-5) on biopsy but will also be analyzed with other definitions provided in Table page 25.

¹ Gleason grading (after Donald F Gleason 1920-2008) is the pathological grading of prostate needle biopsies. Gleason Score is based on recognizing the two most common morphological Gleason grade/pattern under the microscope, a primary and secondary grade, and then summing the two, e.g. 4+3=7. If there are more than two patterns present, and the worst grade is neither the primary nor the secondary grade, GS is based on the predominant + highest grade. The higher the score, the more aggressive the tumor is.

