4 STUDY INTERVENTION

4.1 Intervention

Arm (1) (reference arm)

- Screen-negative: If the total-PSA level is “normal”, i.e. below the cut-off 3.0 ng/mL, no further testing or examination will be performed, but all men will be re-invited.
- Screen-positive: If the total-PSA level is “elevated” above the cut-off i.e. ≥ 3.0 ng/mL, the man will be invited for an MRI.

All men will be recommended standard biopsy, i.e., digital rectal exam followed by TRUS-guided 12-core standard prostate biopsy according to the screening protocol. These standard biopsies will be taken with both the urologist and subject blinded to the MRI result. After these standard biopsies, the study nurse will show the urologist the result from the MRI examination, and in case of suspicious lesion at MRI, 3-4 targeted* biopsies in each of these lesions will be performed in the same séance; 3 targeted biopsies if one of the systematic biopsies already hit the area, and 4 targeted biopsies if otherwise.

- Men in whom MRI for any reason is not achievable or the result is inconclusive will only undergo systematic biopsies

Arm (2) (first experimental arm)

- Screen-negative: If the total-PSA level is “normal”, i.e., below 3.0 ng/mL, no further testing or examination will be performed. The man will be re-invited for screening identical to Arm (1).
- Screen-positive: If the total-PSA level is “elevated” ≥ 3.0 ng/mL, he will be offered MRI.
 - If the MRI is positive (PI-RADS 3-4), only targeted* biopsies will be performed, i.e. 4 biopsy cores targeted against each suspicious lesion, but no systematic biopsies.
 - If the MRI is positive (PI-RADS 5), targeted* biopsies will be performed, i.e., 4 biopsy cores targeted against each suspicious lesion but also systematic biopsies. Changed 2018-10-15 (see amendment 5)
 - If the MRI is negative no biopsies will be performed.
 - If the MRI is negative and PSA ≥ 10 and PSA density (PSAD), ≥ 0.1 , systematic 12-core biopsies will be performed. PSA cut off changed 2016-03-01 from 20 to 10 ng/mL (see amendment 1).
 - Men in whom MRI for any reason is not achievable, or the MRI is technically inferior (for example in men with hip prosthesis), are invited for urological examination with digital rectal examination (DRE) and transrectal ultrasound

(TRUS). These men are included in the intention to screen analysis but not in the per protocol analysis (see 6.2.1).

Arm (3) (experimental arm II)

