5.1 Outcome Ascertainment

The project is planned to run for an initial 4 years with an evaluation of the primary and some of the secondary objectives during year 4. Details of outcomes and times of assessments are given in Table 1 (p 19)

Prostate cancer diagnosis

Reporting of cancer to the National Prostate Cancer Register and the National Cancer Register is mandatory by Swedish law. All diagnoses made in the study will be continuously recorded in the study database. Every 3 months, cross-linkage on the study participants' personal identification number will also be performed with the study database and the cancer registries, to ensure accuracy and completeness of the diagnoses.

Prostate biopsies

One internal pathologist with 25 years of experience of prostate pathology will review the prostate biopsies in the study. To minimize heterogeneity in Gleason grading between different pathologists a secondary review of biopsies with a cancer diagnosis will be conducted by two external pathologists. The reviewers are blinded to the primary local assessment and work independently from each other. Each core harbouring cancer is reviewed separately. The final Gleason score for each patient is based upon these three verdicts. In case of agreement between at least two of the reviewers the Gleason score is set. In case all three reviewers differ from each other the "middle" assessment will be used. In the first screening round the internal pathologist is [name] with 25 years of experience of prostate pathology, and the external pathologists are [name] at Karolinska Institute, Stockholm and [name] at University of Oslo.

Reference for biopsy outcome

For analysing the endpoints based on prostate biopsies, different sets of biopsies will be taken into account (see table below). Adding systematic biopsies at a second occasion in men with cancer detected with targeted biopsies in arms 2 and 3 is an attempt to compensate for possible sampling errors due to the fact that MR positive and MR negative cancers were primarily biopsied with two different techniques. Only systematic biopsies taken within one year after the diagnostic biopsy are taken into account (arms 2 and 3).

If MRI, for any reason, is not achievable or inconclusive, see 4.1

Additional biopsies taken after what here is stated are not considered

Arm 1	Arm, 1	Arm 2 and 3 (PSA < 10 ng/mL or PSA ≥ 10 and PSAD < 0.1)		Arm 2 and 3 (PSA ≥10 ng/mL and PSAD ≥0.1)	

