8.3 Adverse Event Reporting

Adverse events (see toxicity) from MRI and TRUS biopsy will be recorded continuously and summarized once a year. This summary will be discussed within the study board and possibly together with the Advisory board. The study protocol follows principally clinical recommendations from the Swedish Board of Health and Welfare. One critical point in this study is a potential risk to delay diagnosis of serious cancer when omitting biopsy in men with a negative MRI (and a PSA < 10) in Arm 2 and 3. Therefore, analysis of the incidence of interval cancers in these men is planned as well as studying the characteristics of cancers detected at follow-up screens in men with elevated PSA and negative MRI in previous screening rounds. These data will be presented to the Advisory Board for recommendations. No other stopping rules are specified within the protocol.

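### Interval cancers are planned for analysis only in MRI-negative men of arms 2 and 3, so no randomised comparison with arm 1 is stated for the risk the protocol calls critical

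*Protocol*

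**What the plan says.** Section 8.3 (Adverse Event Reporting) identifies, as a critical point, a possible delay in diagnosing serious cancer when "omitting biopsy in men with a negative MRI (and a PSA < 10) in Arm 2 and 3". It answers with two analyses. First, "analysis of the incidence of interval cancers in these men is planned". Second, a study of the "characteristics of cancers detected at follow-up screens in men with elevated PSA and negative MRI in previous screening rounds"; this clause names neither an arm nor a comparator. Both go to the Advisory Board for recommendations, and "No other stopping rules are specified within the protocol".

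Section 2.5 defines the outcomes that compare arm 1 with the MRI-targeted arms. At the first assessment "only screening visits in round 1 are analysed". For the later ones, "Next assessment includes all screening visits up to" 30 June 2022 and then 2, 6 and 10 years on, comparing arm 1 with arm 2. Interval cancer does not appear in the table. Section 6.2.2 treats significant cancer like the primary endpoint but without a test.

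Section 5.1 says that every three months a cross-linkage of study participants "will also be performed with the study database and the cancer registries". Section 4.1 sends arm 1 men above the cut-off to imaging too: "the man will be invited for an MRI".

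**The concern.** Interval cancers also arise after a negative systematic biopsy. A rate in men whose biopsy was omitted therefore cannot show whether the omission delayed diagnosis; that needs the rate in comparable men who were biopsied. The trial has such men by randomisation, in arm 1, but 8.3 does not ask for their rate.

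The monitored group is also mixed. Arm 3 goes to MRI from PSA 1.8 ng/mL, so it contains men at 1.8–2.99 who have no MRI counterpart in arm 1. A single rate over arms 2 and 3 is harder still to read.

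At stake is the usefulness of the only safety information that 8.3 promises the Advisory Board. Alongside it stands the reading of the secondary objective. If arm 2 detects fewer significant cancers at screening, visit-based data do not separate cancers that never surface from those that surface between screens.

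**Working it through.** **1. Which stated analysis could give an interval-cancer contrast with arm 1?**

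| Stated analysis | Compares | Covers interval cancers against arm 1? |
|---|---|---|
| 8.3, interval-cancer incidence | MRI-negative men, PSA <10, arms 2 and 3 | No comparator |
| 8.3, cancers at follow-up screens | PSA-elevated, MRI-negative men; no arm named | No: screen-detected cancers |
| 2.5 and 6.2, first assessment | Arm 1 vs arms 2+3, round 1 visits only | No |
| 2.5 and 6.2, later assessments | Arm 1 vs arm 2, all screening visits | Not stated |
| 3, within-arm 1 comparisons | Biopsy strategies in the same men | No: detection at biopsy |
| 2.5, additional 1 | Arm 2 vs arm 3 | Arm 1 absent |
| 2.5, additional 2 | Screening vs control group, incidence and mortality | Arms not separated |

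No row gives it. Section 5.1 points the same way: it lists the biopsy sets that count for the biopsy endpoints and sets aside any taken later. A clinical biopsy between screens is not listed.

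**2. The plan's own planning figures.** The protocol gives no figure for interval cancers, so only the group sizes can be checked.
- Inputs (6.1): 9% vs 4.5%, two-sided 5%, 80% power; 1:2 allocation for arm 1 vs arms 2+3 (3.5). The pooled-variance formula with continuity correction gives 382 in arm 1 and 3 × 382 = 1,146 in total, against the stated 1,164 (1.5% lower).
- 1,164 / (0.07 × 0.50) = 33,257, against the stated 33,260.

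**3. Men available, from the planning figures.**
- Participants per arm: 36,000 × 0.50 / 3 = 6,000.
- With PSA ≥3 per arm: 6,000 × 0.07 = 420.

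Arm allocation is triggered by delivery of the first PSA result (3.5), so this stratum is fixed before any arm-specific procedure.

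**4. What a randomised contrast could show, under assumed rates.** Arm 1 interval-cancer rates of 0.5%, 1% and 2% among PSA ≥3 men are assumptions. Power = Φ[(d − 1.96·SE0)/SE1], where d is the difference in proportions and SE0 and SE1 are its pooled and unpooled standard errors. Example, 1% vs 2% with 420 per arm: SE0 = 0.00839, SE1 = 0.00838, (0.0100 − 0.0164)/0.00838 = −0.77, power 22%.

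| Assumed arm 1 rate | Expected events, arm 1 | Doubling: arm 1 vs 2 | Doubling: arm 1 vs 2+3 | Tripling: arm 1 vs 2 | Tripling: arm 1 vs 2+3 |
|---|---|---|---|---|---|
| 0.5% | 2.1 | 13% | 12% | 31% | 32% |
| 1% | 4.2 | 22% | 23% | 54% | 62% |
| 2% | 8.4 | 40% | 46% | 84% | 92% |

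Precision for the middle row, 4.2 vs 8.4 expected events: SE(log RR) = √(1/4.2 − 1/420 + 1/8.4 − 1/420) = 0.594. The 95% interval around a ratio of 2 is 2 × exp(±1.96 × 0.594), about 0.6 to 6.4. The contrast is worth having as an estimate but is too weak to carry a test.

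**The case against.** Four points on the other side have force.

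- *Delay is not wholly uncompared.* A reader might infer that delayed diagnosis is never set against arm 1. The documents do not support that. The round 1 comparison of significant cancer is a randomised estimate of detection forgone. A cancer missed then and found at a later screen enters the arm 1 versus arm 2 comparison. This evidence is indirect, because in a cumulative proportion a late detection counts the same as a timely one.
- *Arm 1 MRI-negative men are used.* One might infer that they are ignored. Section 3 uses arm 1's blinded systematic biopsies for within-arm comparisons, which show what a no-biopsy rule would have missed at that visit. They do not show what surfaces between visits.
- *Screening visits only is written for round 1 alone.* For later assessments the text says that screening visits are included; no sentence expressly excludes interval diagnoses. The defensible statement is that their inclusion is not stated.
- *Section 8.3 is a monitoring paragraph, and detail may sit in an analysis plan that is not shown.* That would answer mere silence. But 8.3 fixes the population for its interval-cancer analysis, and 2.5 says that its table gives the details of all outcome definitions.

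It is also fair that the secondary objective concerns detection by screening. Adding interval cancers to an arm's total credits it with cancers that its screening missed and can mask a shortfall. A combined figure can therefore only stand beside the screen-detected one.

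**Conclusion.** The point holds in a limited form. For the risk that the protocol itself calls critical, the interval-cancer analysis it states has no comparator, and the arm 1 comparison is defined by screening visits. No randomised comparison of interval cancers is stated. Later-screen detection and the within-arm 1 comparisons bear on missed cancers but do not supply this contrast.

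This should be changed, but it does not undermine the primary analysis. Its size cannot be given as an event rate, because the documents state none. The power and interval figures rest on assumed arm 1 rates of 0.5–2% and on the planning values of 50% participation and 7% with PSA ≥3. The number of MRI-negative men is not estimated: the documents give no MRI-negative share and no PSA distribution for arm 3 between 1.8 and 2.99.

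**What to change.** In 8.3 and 2.5, state the following.

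1. Interval cancers from registry linkage, and clinically significant or advanced interval cancers, are reported by allocated arm in all men: arm 1 versus arm 2, as estimates with 95% confidence intervals and no test.
2. For the interval after round 1, arm 1 is compared with arms 2 and 3 combined. Cancers in arm 3 men whose round 1 PSA was below 3 are left out, as in the first assessment. Arm 1 and arm 2 men below 3 can also have interval cancers, so the same restriction must apply to them; otherwise the combined arms are undercounted.
3. The PSA ≥3, MRI-negative stratum of each arm is shown as support. Arm 3 men at PSA 1.8–2.99 are shown separately.
4. Screen-detected plus interval significant cancers appear beside the screen-detected figure, never instead of it.

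The cost is protocol wording and a modest analysis, since the three-monthly linkage already covers study participants. The downside is few events and wide intervals. In the all-men comparison, interval cancers below the cut-off, where arms 1 and 2 follow the same pathway, pull the ratio towards 1, so the absolute difference should be reported too.

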- Identical to arm (2) except that the PSA-cut off is lower, ≥ 1.8 ng/mL.

Men in Arm 2 and 3 with cancer diagnosed at targeted biopsies during screening round 1 are recommended completion with systematic biopsies 6-12 weeks after the first biopsy.

* Targeted biopsy = biopsy targeted against MRI positive areas (suspicious for cancer)

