4.4 Special circumstances

Due to high risk of potentially lethal prostate cancer, all men with PSA ≥ 10.0 ng/mL, irrespective of Study Arm, will, for ethical reasons, be recommended 12 standard TRUS-biopsies plus additional targeted biopsies if positive MRI. Exceptions are those with PSAD < 0.1.

On March 1, 2016, the PSA level indicating high risk of lethal prostate cancer was adjusted from ≥ 20.0 ng/mL to PSA ≥ 10.0 ng/mL in order to harmonize with National standardized course of medical care (SVF) for prostate cancer.

Since October 15, 2018, all men with MRI showing a PI-RADS-score 5 in Arm 2 and Arm 3, should, apart from the targeted biopsies, also undergo systematic biopsies with 12 cores. All men with PI-RADS 5 lesions and negative biopsies should be re-evaluated at a radiology conference (round) and, if no adjustment of PI-RADS score, a new set of targeted biopsies should be carried out within 3 months.

The study design is depicted in Figure 1.

5 Study organisation and infrastructure

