MRI pos*	MRI neg	MRI pos **, ***	MRI neg	MRI pos*	MRI neg
12 systematic plus 3-4 targeted biopsies	12 systematic biopsies	4 targeted biopsies. If cancer. 12 additional cores at a later occasion	No biopsies	12 systematic plus 3-4 targeted* biopsies	12 systematic biopsies

- * If the MRI positive sector is sampled with one core in the systematic biopsies, 3 extra targeted biopsies are sampled from that sector, otherwise 4 biopsies
- ** If MRI shows PI-RADS 5, 12 systematic biopsies are added (not in screening round 1)
- ***If cancer is found in the targeted biopsies patients are rescheduled for systematic biopsies

Prostatectomy specimen

Prostatectomy specimen will be processed according to Swedish standard (KVA document) and reviewed at the department of Pathology at Sahlgrenska University Hospital. Tumor volume will be assessed by the planimetric method. Endpoint definitions for prostatectomy specimen are given in table 3, p

Prostate cancer mortality

The project is planned to continue to allow evaluating long-term effects on prostate cancer mortality. In the Göteborg-1 trial [9], an independent Cause of death (COD) committee consisting of 3 urology professors, blinded to study allocation, reviewed the cause of death following a standardized algorithm. A similar COD committee will be used in this study.

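### Section 8.3 follows only MRI-negative men for delayed diagnosis; arm 2/3 men with a positive MRI, benign targeted cores and no systematic cores are not separately followed

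*Protocol*

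**What the plan says.** Section 8.3 calls the possible delay of a serious diagnosis a critical point. It describes that risk for arm 2/3 men who are not biopsied because the MRI is negative and PSA is below 10. It plans the incidence of interval cancers in those men, and "studying the characteristics of cancers detected at follow-up screens in men with elevated PSA and negative MRI in previous screening rounds". Both results go to the Advisory Board, and no other stopping rule is given. Section 9.3.1 mentions close follow-up for delayed diagnosis and points to 8.3 without naming another population.

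The pathway in sections 4.1 and 5.1 omits systematic cores in a second place. For arm 2 men with PI-RADS 3-4, "only targeted* biopsies will be performed, i.e. 4 biopsy cores targeted against each suspicious lesion, but no systematic biopsies". Arm 3 is "Identical to arm (2) except that the PSA-cut off is lower, ≥ 1.8 ng/mL". Later systematic cores depend on a cancer finding: "Men in Arm 2 and 3 with cancer diagnosed at targeted biopsies during screening round 1 are recommended completion with systematic biopsies 6-12 weeks" (counted from the first biopsy). The biopsy reference table in 5.1 agrees for MRI-positive arm 2/3 men with PSA below 10, or PSA of 10 or more with PSAD below 0.1: "4 targeted biopsies. If cancer. 12 additional cores at a later occasion".

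**The concern.** The strategy under test drops systematic cores in two ways: no biopsy when the MRI is negative, and targeted cores only when it is positive. A PI-RADS 3-4 man in arm 2 or 3 with benign targeted cores leaves the visit without systematic sampling. His arm 1 counterpart is recommended 12 systematic cores as well as the targeted ones. If a significant cancer lay outside the sampled lesion, or the targeted cores missed the lesion, its diagnosis is delayed by the strategy.

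Section 8.3 ties its safety analyses to only the first kind of omission. At stake is what the Advisory Board sees. A cluster of interval or next-round cancers after benign targeted biopsies would not appear in the one report that the protocol sets aside for delayed diagnosis.

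**Working it through.** **Step 1. Who in arms 2/3 lacks systematic cores, and does 8.3 follow them?**

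| Pathway | Systematic cores | In the 8.3 analyses |
|---|---|---|
| MRI negative, PSA below 10 | None | Yes |
| MRI positive, cancer in targeted cores (round 1) | Recommended later | Not applicable, already diagnosed |
| PI-RADS 3-4, benign targeted cores, PSA below 10 or PSAD below 0.1 | None | No |
| PI-RADS 5, benign targeted cores | Depends on date or round | No |
| PSA 10 or more and PSAD 0.1 or more | 12 cores | Not an omission |

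For PI-RADS 5, section 4.4 adds 12 systematic cores from October 15, 2018 without naming a round. The footnote to the table in 5.1 reads "If MRI shows PI-RADS 5, 12 systematic biopsies are added (not in screening round 1", and section 9.3.1 places the end of round 1 in 2021. The text therefore does not settle how many PI-RADS 5 men had no systematic cores, and these statements should be reconciled. Section 4.4 also sends PI-RADS 5 men with negative biopsies to radiological re-evaluation and, if the score stands, repeat targeted biopsy. No such step is stated for PI-RADS 3-4.

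**Step 2. Does another analysis follow the third row?**

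- *Within-arm-1 comparisons (section 3).* They estimate what systematic cores add to targeted cores in MRI-positive men at round 1. Those men had the cores taken, and there is no follow-up.
- *Later arm 1 versus arm 2 comparisons (2.5, 6.2.1).* They cover all men in the two arms, defined by screening visits. Next-screen cancers enter, but pooled over pathways, and interval cancers may be left out. If counting is cumulative, a significant cancer missed in round 1 and found in round 2 adds to arm 2's detection and is not marked as late.
- *Arm 3.* Its men are not in the later arm 1 comparison. They are compared with arm 2, which omits the same cores.
- *Registry linkage (5.1).* It runs every 3 months, so the diagnoses are available. No analysis of them by this pathway is stated.

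**Step 3. Size of the group.**

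Inputs from section 6.1: 7% of attenders with PSA of 3 or more, 50% participation, 36,000 in the screening group. From 3.5: 1:1:1 allocation. The plan's own step reproduces: 1,164 / (0.07 × 0.50) = 33,257, stated as 33,260.

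Men with PSA of 3 or more in arms 2+3: 36,000 × 0.50 × 0.07 × 2/3 = 840.

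Assumptions, not in the protocol: a proportion *m* is MRI-positive, and a proportion *b* of those have benign targeted cores.

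- Group (b), MRI-positive and benign: 840 × *m* × *b*
- Group (a), MRI-negative: 840 × (1 − *m*)
- Share of (b) among both = *mb* / (1 − *m* + *mb*)

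| *m* | *b* | Group (b) | Group (a) | Share of (b) |
|---|---|---|---|---|
| 0.30 | 0.40 | 101 | 588 | 101/689 = 15% |
| 0.35 | 0.50 | 147 | 546 | 147/693 = 21% |
| 0.40 | 0.60 | 202 | 504 | 202/706 = 29% |

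Starting from 1,164 × 2/3 = 776 men, with *m* from 0.25 to 0.45 and *b* from 0.30 to 0.70, group (b) is 58 to 244 men and the share 9% to 36%.

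These counts assume that every man with PSA of 3 or more has the MRI and every MRI-positive man is biopsied. The PI-RADS 5 and PSA 10 exceptions are not subtracted. Arm 3 men with PSA 1.8-2.99 are not counted and would add to both groups.

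**The case against.** The strongest reply is that nothing here is an error. Section 8.3 is the adverse-event section, it flags one critical point without claiming to be exhaustive, and a breakdown by pathway could sit in an analysis plan that is not shown. It is true that no contradiction is involved and that no endpoint, test or sample size changes. But the protocol itself fixes the population of these analyses and links it to Advisory Board review, and that population covers one of the two omissions.

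Some stronger readings are tempting, and the protocol does not support them.

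- *These men are not examined at all.* A reader might infer this from 8.3 alone. Section 3 measures the round 1 yield of added systematic cores in MRI-positive arm 1 men, and later comparisons include the arm 2 men in aggregate. What is missing is separate follow-up for delayed diagnosis.
- *Their cancers will not count against the strategy.* Next-screen cancers in arm 2 are included in the later comparison. They are just not identified as delayed.
- *They are at higher risk than the MRI-negative men who are followed.* A positive MRI raises risk before biopsy. The relevant comparison is risk after benign targeted cores against risk after a negative MRI, and the protocol gives neither.
- *The gap covers all MRI-positive men with benign cores.* Men with PSA of 10 or more and PSAD of 0.1 or more are recommended systematic cores, and PI-RADS 5 is partly handled.

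**Conclusion.** The point stands in a limited form. The delayed-diagnosis data that 8.3 routes to the Advisory Board cover arm 2/3 men with a negative MRI only. Arm 2/3 men with a positive MRI, benign targeted cores and no systematic cores are not separately followed. That much rests on the text and needs no figure.

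The size does need assumed rates. About 100 to 200 men, or 15-29% of those with omitted systematic cores, follow from the narrower assumptions, and 9-36% from the wider ones. A single figure such as one in five would claim more than the protocol allows. Nothing here shows that the primary comparison is biased or that the pathway is unsafe. It is a worthwhile, inexpensive correction to safety monitoring.

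**What to change.** In section 8.3, define the population of both analyses, and of the Advisory Board report, as all arm 2/3 men in whom systematic biopsies were omitted:

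- (a) MRI-negative without biopsy;
- (b) MRI-positive with benign targeted cores and no systematic cores.

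Report interval cancers and the characteristics of cancers at follow-up screens for (a), for (b), and for both together. Classify men by the cores actually taken, so that the PI-RADS 5 and PSA 10 exceptions sort themselves out. Show arm 3 men with PSA 1.8-2.99 as a separate line.

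The cost is a change of wording and one more analysis group from data already recorded and linked. Group (b) will probably have few events, so its estimates will be imprecise and should be given with confidence intervals and no test. No procedure, visit or biopsy rule changes.
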